6.2.5 Conventions for Missing and Partial Dates

All rules explained below for partial/missing dates will be followed unless contradicted by any other data recorded on the electronic Case Report Form (eCRF).

All dates presented in the individual subject listings will be as recorded on the eCRF (i.e., not completed as per the below rules).

6.2.6 Missing / Partial Start / Stop Date of Adverse Events (AE) and Concomitant Medications

Missing and partial start and stop dates will be imputed for analysis purposes as follows:

Partial or missing stop date will be imputed as follows:

- If the stop date is completely missing and the event has resolved or the subject has stopped taking the concomitant medication, the stop date will be imputed as the date of the subject’s last clinic visit in the study.
- If only the year is known, the stop date will be imputed as “31-Dec” of that year or as the date of the subject’s last clinic visit in the study if in the same year.

QMD Ref: [REDACTED]	Effective: 12Aug2019	Governing QMD: [REDACTED]
Confidentiality Statement		
This document is the property of [REDACTED] and may not be duplicated, copied, altered or removed from company without prior approval from [REDACTED] or in compliance with [REDACTED].		

REF: [REDACTED]

		Controlled Quality Management Document	
		Sponsor:	Aurinia Pharmaceuticals
		Protocol Number:	AUR-VCS-2016-02
STATISTICAL ANALYSIS PLAN. PHASE 2-3-4			

- If the month and year are known, the stop date will be imputed as the last day of that month unless the stop date corresponds to the same month as the subject’s last clinic visit in which case the date of subject’s last clinic visit in the study will be used instead.

Missing start date will be imputed as follows:

- If the stop date occurs on or after the start of study drug in AURORA 2 or the event/concomitant medication is ongoing, the start date will be imputed as the date of the first dose of study drug in AURORA 2.
- If the stop date occurs before the start of study drug in AURORA 2, the start date of the event/concomitant medication will be imputed as the subject’s AURORA 1 Visit 15 (Week 52) date or the stop date of the event/concomitant medication whichever the earlier.

Partial start date (year present, but month and day missing)

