- If the stop date occurs on or after the start of study drug in AURORA 2 or the event/concomitant medication is ongoing at the end of AURORA 1, and the year is the same as the year of first dosing in AURORA 2 the start date will be imputed as “01-Jan” of the same year or the date of the first dose of study drug in AURORA 2 whichever is latest. If the year is different from the year of first dosing “01-Jan” will be used.

If the stop date occurs before the start of study drug in AURORA 2, the start date of the event/concomitant medication will be imputed as the “01-Jan” of the same year.

Partial start date (month and year present, but day missing)

- If the stop date occurs on or after the start of study drug in AURORA 2 or the event/concomitant medication is ongoing, the start date will be imputed as the first day of the same month and year unless this partial start date is in same month as the first dose of study drug in AURORA 2 in which case the date of first dose of study drug in AURORA 2 will be used.

If the stop date occurs before the start of study drug in AURORA 2, the start date will be imputed as the first day of the month and year of the partial stop date.

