6.11.1 Efficacy Endpoint

Renal response is defined as:

- UPCR of ≤ 0.5 mg/mg
- eGFR criteria:
 - eGFR ≥ 60 mL/min/1.73 m² or
 - eGFR < 60 mL/min/1.73 m² with no confirmed decrease $> 20\%$ or
 - eGFR < 60 mL/min/1.73 m² with confirmed decrease $> 20\%$ but with no disease-related or treatment-related eGFR associated AE present at time of assessment
- Received no rescue medication for LN
- Did not receive more than 10 mg prednisone for ≥ 3 consecutive days or for ≥ 7 days in total during the 8 weeks prior to the renal response assessment.

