6.11.7 Other Secondary Endpoints

Not applicable.

QMD Ref: [REDACTED]	Effective: 12Aug2019	Governing QMD: [REDACTED]
Confidentiality Statement		
This document is the property of [REDACTED] and may not be duplicated, copied, altered or removed from company without prior approval from [REDACTED] or in compliance with [REDACTED].		
REF: [REDACTED]		Page 27 of 37

		Controlled Quality Management Document	
		Sponsor:	Aurinia Pharmaceuticals
		Protocol Number:	AUR-VCS-2016-02
STATISTICAL ANALYSIS PLAN. PHASE 2-3-4			

A treatment-related TEAE is defined as a TEAE that is assessed by the Investigator or Sponsor as being related to study drug. If a TEAE has a missing relationship to study drug it is assumed to be related to the study drug for analysis purposes.

A disease-related TEAE is defined as a TEAE that is assessed by the Investigator or Sponsor as being related to the disease under study. If a TEAE has a missing relationship to the disease under study it is assumed to be related to the disease under study for analysis purposes.

Missing severity assessments will be summarised as severe.

Adverse event tables will comprise tables summarizing AURORA 2 TEAEs as well as some tables summarizing all TEAEs from month 0 to month 36.

The following tables will be presented for AURORA 2 TEAEs:

- Summary table of overall incidence, the number of events, relative risk and 95% CI (voclosporin:placebo) including the following top line summaries:
 - Any AE
 - Any TEAE
 - Any Treatment-Related TEAE
 - Any Serious TEAE
 - Any Treatment-Related Serious TEAE
 - Any TEAE Leading to Voclosporin/Placebo Modification
 - Any TEAE Leading to Voclosporin/Placebo Discontinuation
 - Any TEAE Resulting to Death
 - Disease-Related TEAE
 - Disease-Related Serious TEAE
- TEAEs by System Organ Class and Preferred term
- TEAEs by System Organ Class, Preferred term and severity
- Treatment-Related TEAE by System Organ Class and Preferred Term
- Treatment-Related TEAE by System Organ Class, Preferred Term and Severity
- TEAE by System Organ Class and Preferred Term Leading to Dose Modification
- TEAE by System Organ Class and Preferred Term Leading to Voclosporin/Placebo Discontinuation
- TEAE by System Organ Class and Preferred Term Resulting in Death
- Disease-Related TEAE by System Organ Class and Preferred Term
- Serious TEAE by System Organ Class and Preferred Term

QMD Ref: [REDACTED]	Effective: 12Aug2019	Governing QMD: [REDACTED]
Confidentiality Statement		

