6.12.1.1 Exposure-Adjusted Incidence Rates

Tables showing the overall incidence rate, total number of subjects with a given event and total events per 100 years exposure will be produced. These tables will incorporate all events from AURORA 1 and AURORA 2.

All AEs will be listed.

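### SAP 6.2.6 replaces a known start month with the stop month for some records ending before AURORA 2, probably through a slip of stop for start

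*SAP*

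**What the plan says.** The SAP 6.2.6 heading is "Missing / Partial Start / Stop Date of Adverse Events (AE) and Concomitant Medications". Under its sub-heading "Partial start date (month and year present, but day missing" there are two branches:

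- **Record stops on or after the start of AURORA 2 dosing, or is ongoing:** "the start date will be imputed as the first day of the same month and year". The exception is a start in the month of the first AURORA 2 dose, where that dose date is used.
- **Record stops before AURORA 2 dosing:** "the start date will be imputed as the first day of the month and year of the partial stop date".

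For incomplete stop dates with a known month, "the stop date will be imputed as the last day of that month", or the last clinic visit if that falls in the same month. SAP 6.2.8, on diagnosis dates, keeps the recorded month and sets the day to the first. SAP 6.2.5 lets all these rules yield to contradicting eCRF data.

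Several outputs use records from before AURORA 2. The adverse-event section plans "some tables summarizing all TEAEs from month 0 to month 36" and displays by year of onset that start from AURORA 1. For the exposure-adjusted rates in 6.12.1.1, "These tables will incorporate all events from AURORA 1 and AURORA 2". SAP 6.11.2.1 analyses renal response at Months 6 and 12 as well as later. SAP 6.11.1 limits prednisone above 10 mg to fewer than 3 consecutive days and fewer than 7 days "in total during the 8 weeks prior to the renal response assessment".

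**The concern.** The sub-heading says that the start month is known, yet the second branch ignores it and takes the month from the other end of the record. A programmer who follows the text would overwrite good data.

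Two results could be affected. First, an event that began before the first AURORA 1 dose and ended during AURORA 1 can be given an onset after that dose and be counted as treatment-emergent. Second, a steroid course can be shortened or moved, so that a subject who failed the steroid criterion at Month 6 appears to pass it.

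**Working it through.** The plan gives no figure to reproduce, so the check applies the rule as written and as probably intended to the same records. All example dates are illustrative assumptions.

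**Definitions**
- Start as written = day 1 of the stop month. Start as corrected = day 1 of the recorded start month.
- Duration = stop − start + 1.
- Treatment-emergent from AURORA 1 if start ≥ first AURORA 1 dose (assumed cut-off).
- Days in window = min(stop, visit − 1) − max(start, visit − 56) + 1, not below 0. The 56 days are the 8 weeks of SAP 6.11.1.

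**Size of the shift.** Start as written minus start as corrected, over all calendar months of 2017 to 2019:
- same month: 0 days
- one month apart: 28 to 31 days
- two months apart: 59 to 62 days
- three months apart: 89 to 92 days

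The shift is never negative. When the months differ, the imputed duration is at most the length of the stop month.

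**Examples.** First AURORA 1 dose 10 March 2018, Month 6 visit 10 September 2018, so the window is 16 July to 9 September. Steroid courses are taken as above 10 mg.

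| Record (start month to stop) | As written | As corrected |
|---|---|---|
| AE, Feb to 20 Apr | start 1 Apr, 20 days, TEAE | start 1 Feb, 28+31+20 = 79 days, pre-treatment |
| Steroid, Jul to 2 Sep | start 1 Sep, 2 days in window | start 1 Jul, 16+31+2 = 49 days in window |
| Steroid, Jul to 20 Aug | start 1 Aug, 20 days in window | start 1 Jul, 16+20 = 36 days in window |
| Steroid, Aug to 5 Oct | start 1 Oct, 0 days in window | start 1 Aug, 31+9 = 40 days in window |
| Steroid, Aug to Oct (day missing, taken as 31 Oct) | start 1 Oct, 0 days in window | start 1 Aug, 40 days in window |

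**Reading the table**
- The AE changes from pre-treatment to treatment-emergent. This happens whenever the true onset precedes the first AURORA 1 dose and day 1 of the stop month is on or after it.
- The course ending 2 September drops to 2 days, below both the 3-day and 7-day limits, so it no longer fails the criterion.
- The course ending 20 August still has 20 days, so nothing flips. A course that stops before the visit, on day 3 or later of a month inside the window, keeps at least 3 consecutive days.
- A course running past the visit into a later month gets a start after the visit and leaves the window entirely.

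**What cannot change.** For affected records, day 1 of the stop month ≤ stop date < first AURORA 2 dose. Protocol 13.9 counts AURORA 2 TEAEs from that dose, so none is created or lost. An 8-week look-back from Month 18 or later does not reach a course that stopped before AURORA 2 dosing.

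**The case against.** The case on the other side has five parts.

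- **It is an obvious slip.** The adjacent branch and 6.2.8 keep the recorded month. This stands, and it makes the sentence easy to correct. Until then, the text is still what gets programmed.
- **The eCRF override in 6.2.5 protects the recorded month.** A recorded start in February arguably contradicts an imputed start in April. But the clause supplies no replacement date, so it softens the rule without repairing it.
- **The rule may apply only to incomplete stop dates.** On that narrow reading the stop normally becomes month-end, and the route through a course ending on day 1 or 2 closes. The TEAE misdating and the course that runs past the visit both survive.
- **The data path is uncertain.** SAP 6.9 also treats oral corticosteroids as exposure, and no text says that the 10 mg criterion uses dates from 6.2.6. SAP 6.2 leaves derived source variables alone unless otherwise stated, so AURORA 1 dates or flags may already be fixed. The visible TEAE definition, in protocol 13.9, covers AURORA 2 only. These points stand as limits on the effect.
- **Steroid flips are rare.** They need specific dates and a subject who meets every other response criterion. Month 12 leaves little room, because that visit is entry to AURORA 2 and the course must still stop before AURORA 2 dosing. Month 6 is an SAP time point that protocol 13.7.2.1 does not list. This stands.

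A reader might infer that everything ending before AURORA 2 is misdated, always too late and too short. The documents do not support that. Records with a complete start date fall outside this rule. Where start and stop share a month, the rule gives day 1 of that month, which is never later than the true start.

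**Conclusion.** The sentence is wrong as written and should be corrected. For records with a missing start day, a stop before AURORA 2 dosing, and different start and stop months, it moves the start to a later month and cuts the duration to at most one calendar month. This can add TEAEs to the Month 0 to 36 and year-of-onset tables, and to the exposure-adjusted rates if those count treatment-emergent events only. That assumes onset is compared with the first AURORA 1 dose using dates imputed under 6.2.6. If steroid courses are also dated this way, the steroid criterion can flip towards response at Month 6, and rarely at Month 12, by the two routes shown.

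A reader might infer that the treatment comparison or the AURORA 2 safety results are biased. The documents do not show this: the rule is the same in both arms, the number of affected records is not given, and AURORA 2-only TEAE counts and Month 18 to 36 response are untouched. The size of any effect cannot be computed from the documents.

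**What to change.** In the last sentence of SAP 6.2.6, change *partial stop date* to *partial start date*, so that the imputed start is day 1 of the recorded start month and year. This matches the adjacent branch and 6.2.8. The cost is one word in the SAP and, if the rule is already programmed as written, one line of code and a rerun of the affected outputs. No new data are needed.

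How to treat a start in the same month as the first AURORA 1 dose is a separate, debatable question. A first-dose comparison for AURORA 1 should not be added as part of this correction.

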6.2.7 Missing Last Dates of Study Drug Dosing

If the date of last dose of study drug is completely missing, then the date of last dose of study drug will be taken for analysis purposes as the date when the subject would have run out of study

QMD Ref: [REDACTED]	Effective: 12Aug2019	Governing QMD: [REDACTED]
Confidentiality Statement		
This document is the property of [REDACTED] and may not be duplicated, copied, altered or removed from company without prior approval from [REDACTED] or in compliance with [REDACTED].		

REF: [REDACTED]

		Controlled Quality Management Document	
		Sponsor:	Aurinia Pharmaceuticals
		Protocol Number:	AUR-VCS-2016-02
STATISTICAL ANALYSIS PLAN. PHASE 2-3-4			

drug assuming full compliance from the date the study drug was last dispensed or the date of subject's last clinic visit in the study or early withdrawal or death whichever is earlier.

If only the month and year of the last dose was recorded, then the date of last dosing will be taken for analysis purposes as the date the subject would have run out of study drug assuming full compliance from the date the study drug was last dispensed, the last day of the month of the recorded last dose or the date of subject's last clinic visit in the study or early withdrawal or death whichever the earlier.

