- 24-hour urine collection at Month 12, provided from the results of Week 52/ End of Treatment Visit of the AURORA 1 study, and at Months 18, 24, and 30 (**IMPORTANT:** 24-hour urine collection will have to begin 2 days prior to the scheduled visit in order not to coincide with the FMV sampling due on the day of this visit).
- Pregnancy testing and immunology at all visits; serum pregnancy testing at Month 12 and Month 24 and urine pregnancy testing at Month 12, Month 15, Month 18, Month 21, Month 27, Month 30, and Month 33.
- AEs at all visits; Month 12 assessments will be provided from the results of Week 52/ End of Treatment Visit of the AURORA 1 study.
- Concomitant medications at all visits; Month 12 assessments will be provided from the results of Week 52/ End of Treatment Visit of the AURORA 1 study.
- SELENA-SLEDAI will be evaluated at Month 12, provided from the results of Week 52/ End of Treatment Visit of the AURORA 1 study, and at Months 18 and 24.
- Study treatment dispensing (including study treatment and background therapy) at all visits.
- Returned capsule count and drug accountability at all visits.
- Information for the HRU assessment will be collected and recorded at all visits; Month 12 assessments will be provided from the results of Week 52/ End of Treatment Visit of the AURORA 1 study.
- 

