6.9 Exposure to Study Drug

Overall exposure to study drugs (number of days of exposure to study drugs and mean dose) will be presented for both the safety populations. Exposure will be based on prescribed dose. Exposure will not be summarized by visit but for the overall study duration in AURORA 1 and AURORA 2. Overall study drug exposure will be calculated from the first dose date in AURORA 1 to the last dose date in AURORA 2 plus 1. Care should be taken to not double-count days. It is expected that prescription records will cover each study day between randomization and the end of study (or early termination). Periods of zero dose will be assigned as such.

The following gives an example of a subject with 5 prescription records over the 3-year (1095 day) period.

Final prescription records that detail a zero dose will be removed.

Table 5.1 Exposure calculation example

Start Day	End Day	Dose (bid)	Duration
1	364	3	364 days
365	500	3	136 days
501	600	0	100 days
601	750	2	150 days
751	1095	3	345 days

For the purposes of analysis this subject will have ‘days on treatment’ calculated as 364+136+100+150+345=1095 days. Their mean daily dose will be:

$(364*3 + 136*3 + 100*0 + 150*2 + 345*3) / 1095 = 2.34$ caps BID (converted to 37.03mg per day).

Gaps between dosing records will be counted as a zero dose.

For subjects who are lost to follow-up, and for whom the last dose date from the termination record is unknown, the date of the last available visit will be used as the last dose date.

QMD Ref: [REDACTED]	Effective: 12Aug2019	Governing QMD: [REDACTED]
Confidentiality Statement		
This document is the property of [REDACTED] and may not be duplicated, copied, altered or removed from company without prior approval from [REDACTED] or in compliance with [REDACTED].		
REF: [REDACTED]		

		Controlled Quality Management Document	
		Sponsor:	Aurinia Pharmaceuticals
		Protocol Number:	AUR-VCS-2016-02
STATISTICAL ANALYSIS PLAN. PHASE 2-3-4			

Exposure to study drug will be summarized for the following:

- Voclosporin
- MMF
- Oral Corticosteroids.

Prescribed dose changes at visit intervals and overall will be summarized for voclosporin/placebo and for MMF.

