This document is the property of [REDACTED] and may not be duplicated, copied, altered or removed from company without prior approval from [REDACTED] or in compliance with [REDACTED].		

REF: [REDACTED]

		Controlled Quality Management Document	
		Sponsor:	Aurinia Pharmaceuticals
		Protocol Number:	AUR-VCS-2016-02
STATISTICAL ANALYSIS PLAN. PHASE 2-3-4			

- Serious TEAE by System Organ Class, Preferred Term and Severity
- Treatment-Related, Serious TEAE by System Organ Class and Preferred Term
- Treatment-Related, Serious TEAE by System Organ Class, Preferred Term and Severity
- Serious TEAE by System Organ Class and Preferred Term Leading to Dose Modification
- Serious TEAE by System Organ Class and Preferred Term Leading to Voclosporin/Placebo Discontinuation
- Disease-Related, Serious TEAE by System Organ Class and Preferred Term

The following displays of AURORA 2 TEAEs will also be presented:

- Treatment-Emergent Adverse Events by Descending Frequency of Preferred Term
- Non-Serious Treatment-Emergent Adverse Events Occurring at an Incidence of >2% by Descending Frequency, System Organ Class and Preferred Term
- Treatment-Emergent Adverse Events by Descending Difference of Preferred Term between Treatment Group
- Listing of Serious TEAE
- Listing of TEAE Resulting in Death
- Listing of Post-Treatment Adverse Events Resulting in Death

The following displays will include all TEAEs from the start of AURORA 1:

- TEAE by System Organ Class and Preferred Term by Year of Onset
- Treatment-Related TEAE by System Organ Class, Preferred Term and Year of Onset
- TEAE by System Organ Class and Preferred Term Leading to Dose Modification by year of onset
- Serious TEAE by System Organ Class and Preferred Term by Year of Onset
- Treatment-Related, Serious TEAE by System Organ Class and Preferred Term and Year of onset
- Serious TEAE by System Organ Class and Preferred Term Leading to Dose Modification by year of onset

The following displays will be presented for all randomized subjects from Aurora 1?

- TEAE by System Organ Class and Preferred Term
- Serious TEAE by System Organ Class and Preferred Term

QMD Ref: [REDACTED]	Effective: 12Aug2019	Governing QMD: [REDACTED]
Confidentiality Statement		
This document is the property of [REDACTED] and may not be duplicated, copied, altered or removed from company without prior approval from [REDACTED] or in compliance with [REDACTED].		

REF: [REDACTED]

		Controlled Quality Management Document	

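### For a subject who dies or is lost between visits with no last-dose date, SAP 6.2.7 read literally imputes the day the last supply was dispensed, and a partly known date can be imputed before its recorded month

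*SAP*

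**What the plan says.** SAP 6.2.7 has two rules.

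- **Last-dose date completely missing.** One candidate is the date on which the subject would have run out of study "drug assuming full compliance from the date the study drug was last dispensed". The others are the "last clinic visit in the study or early withdrawal or death whichever is earlier".
- **Month and year known.** The candidates are the same, plus "the last day of the month of the recorded last dose". The selection rule is again "last clinic visit in the study or early withdrawal or death whichever the earlier".

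SAP 6.9 has a separate rule for subjects lost to follow-up whose last-dose date is not on the termination record: "the date of the last available visit will be used as the last dose date".

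SAP 6.2.5 qualifies the date conventions in general. They "will be followed unless contradicted by any other data recorded on the electronic Case Report Form".

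Protocol 9.2.2 provides for "Study treatment dispensing (including study treatment and background therapy) at all visits", and protocol 4.1 places those visits three months apart. In the Schedule of Events, Visit 23 (Month 36) is for compliance only. Among its adverse event displays, the SAP has tables of TEAEs resulting in death and a separate "Listing of Post-Treatment Adverse Events Resulting in Death".

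**The concern.** A subject on treatment leaves each quarterly visit with a new supply. If that subject dies or disappears before attending again, the last clinic visit is the dispensing visit. Run-out and death both lie later, so the minimum treats dosing as having stopped on the day the new supply was handed out. The rule names death as a candidate, but a death date cannot precede the last clinic visit, so it never determines the answer.

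The last-dose date feeds exposure (SAP 6.2.9 and 6.9). It may also feed the line between treatment-emergent and post-treatment events. The AE profile is the primary endpoint. Fatal TEAEs appear in the overview table with a relative risk and in a table by system organ class and preferred term. In the visible text, fatal post-treatment AEs have only a listing of their own. In a safety population of 216, one or two fatal events on the wrong side of that line could alter the fatal-TEAE comparison.

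**Working it through.** The plan gives no figure to reproduce here, so the rule was applied to worked cases.

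**Inputs**
- Rule: minimum of run-out, last clinic visit, withdrawal and death, using those that exist (SAP 6.2.7).
- Visit spacing: three months, taken as 91 days; 71 to 111 days with the ±10-day windows (Schedule of Events).
- Pack size: 168 capsules per carton (protocol 7.5.2). At 3 capsules BID, 168 / 6 = 28 days.
- Supply per visit: not stated. Assumed 3 to 4 cartons, so 3 × 28 = 84 to 4 × 28 = 112 days.

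**Missing date.** Day 0 is the last dispensing visit.

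| Case | Last clinic visit | Result of 6.2.7 |
|---|---|---|
| Dies day 60, no later visit | day 0 | day 0 |
| Lost to follow-up, no later visit | day 0 | day 0 |
| Dies day 60, unscheduled visit day 14 | day 14 | day 14 |
| Withdraws day 60 with early termination visit that day | day 60 | day 60 |
| Stops drug, attends visits to day 400 | day 400 | run-out (day 84 to 112) |
| Completer, Visit 23 day 91, Visit 24 day 121 | day 121 | run-out (day 84 to 112) |

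The result is the dispensing day only in the first two rows. The third row shows that an intervening visit without dispensing still cuts a day-60 death back to day 14.

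**Exposure dropped in the first row.** At most about 91 days, which is 91 / 730 = 12.5% of the 24-month period. The mean is 91 / 2 = 45.5 days if deaths are uniform over the interval.

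**Month and year known.** Last visit and dispensing 10 April, last dose recorded as June. Run-out falls between 3 July (84 days) and 31 July (112 days), and the last day of the recorded month is 30 June. The minimum is 10 April. From 10 April to 1 June is 20 + 31 + 1 = 52 days, so the imputed date lies 52 days before the recorded month begins.

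**Possible reclassification.** The end of the TEAE period is not in the SAP text available for review, so windows of 14, 30 and 60 days are assumed. With death uniform over 91 days, imputed last dose on day 0, window w and onset-to-death lag L, the share of fatal events starting after the window is (91 − w − L) / 91.

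| Window w | L = 0 | L = 14 |
|---|---|---|
| 14 days | 77/91 = 85% | 63/91 = 69% |
| 30 days | 61/91 = 67% | 47/91 = 52% |
| 60 days | 31/91 = 34% | 17/91 = 19% |

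For w = 30 and L = 0, visit intervals of 71 and 111 days give 41/71 = 58% and 81/111 = 73%. These shares apply only to fatal events in subjects who have no last-dose date and no later visit.

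**The case against.** A reader might infer that the rule always returns the last visit and that run-out never applies. The documents do not support that. Withdrawing subjects are advised to attend Visits 23 and 24, subjects who stop drug keep attending, and completers have Visit 24. An unscheduled visit is required two weeks after a dose reduction. In these cases another date governs, as the worked cases show.

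A reader might also infer that deaths will drop out of the primary safety comparison. That is not shown. The only visible TEAE definition, in protocol 13.9, has a start bound and no end, and under it no death would be reclassified. The separate post-treatment listing makes an end window plausible but does not establish one. Protocol 13.9 also summarises SAEs occurring at any time after consent and SAEs that led to death. The exposure-adjusted tables (SAP 6.12.1.1) take in all events from both studies, so a fatal event would stay in those outputs.

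The wording allows another reading, in which run-out is compared with a single end-of-participation date: visit, withdrawal or death, whichever applies. A death on day 60 would then give day 60. If that is meant, the text should say so. That reading still leaves 10 April in the June example wherever the last visit is the applicable end date.

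The override in 6.2.5 is a real safeguard for partial dates, since a recorded June contradicts 10 April. It blocks that date but supplies no replacement. It helps with a completely missing date only if other eCRF data bear on dosing. SAP 6.9 expects prescription records to cover each study day, so missing dates may be few.

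Finally, imputing to run-out assumes full compliance after last contact and could add up to 112 unobserved days. Stopping at the last visit shortens the denominator and so raises exposure-adjusted rates. For subjects lost to follow-up this is a fair argument for the last-visit convention, and it stands.

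**Conclusion.** The defect is narrow but identifiable. It concerns subjects with no complete last-dose date and no clinic visit after the last dispensing, in practice those who die or are lost between quarterly visits. For them the literal rule in 6.2.7 returns the dispensing day. When month and year are recorded, the same minimum can precede the recorded month, with no stated replacement.

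The size is up to about 91 days of probable dosing per affected subject, given quarterly visits and enough supply to reach the next one. Movement of a fatal event from the TEAE tables to the post-treatment listing is possible, but it depends on an end window that cannot be seen. The percentages above illustrate assumed windows and are not estimates for this trial. The number of affected subjects cannot be derived from the documents and may be small. The point still merits correction before database lock, because it touches the primary safety endpoint and the rule cannot use a death date even when one is known.

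**What to change.** - **Deaths (6.2.7).** For a subject who dies while still holding dispensed drug, use the earlier of run-out and death, and leave the last clinic visit out of the minimum. Basing the test on drug still held, and not only on dispensing at that visit, also covers the unscheduled visit on day 14. A death on day 60 then gives day 60 for any supply of 84 to 112 days.
- **Partial dates (6.2.7).** When month and year are recorded, never impute a date before the first day of that month.
- **Lost to follow-up (6.2.7 and 6.9).** State one rule in both places. The two now differ if a subject stops drug, attends visits past run-out and is then lost: 6.2.7 gives run-out and 6.9 gives the later visit. Whether the common rule is last visit or run-out is a judgement, and the last-visit convention may be kept.

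The cost is a few sentences in the SAP and one derivation. The downside is slightly longer imputed exposure for a subject who stopped drug some time before death.
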